3.6.2 Qualitative data outcomes

Data collected from focus group discussions and key informant interviews will be triangulated with quantitative data to address:

- (1) Adolescents' knowledge, Attitudes and Practices towards RH and pregnancy related services
- (2) Health care providers' attitude towards adolescent RH services, perception of adolescents' attitudes towards pregnancy, RH services and challenges for adolescents follow up in the current ANC and post-delivery care
- (3) Effect of adolescents' HIV/STI risk perception and motivation to utilize services including condom use

3.7 Statistical considerations and analysis plan

3.7.1 Sample size determination

Sample size determination

Sample size for this study was based on the outcomes, uptake of effective contraceptive, or prevalence of STIs, at last follow-up comparing each of the two interventions to the control in this three-arm trial. We assumed the uptake of effective contraceptives and consistent condom use as a composite outcome to be 10% [38] (in control/standard), 30% and 35% at the last follow-up in the two intervention arms. At 80% power, and 5% type 1 error rate, and a 10% loss to follow-up, the sample size in the intervention arms was 100 (each 50), while the control/standard was adjusted to 71; this follows a recommendation by Fleiss et al for multiple-arm trials that control arms have a bigger sample size than the intervention.

For the prevalence of STIs, we assumed 20%[10] in control/standard arm, 10% in the intervention-1, and 8% in intervention-2 at the last follow-up, suggesting an average of 55% reduction in prevalence of STI. With similar power of 80%, 5% type-1 error rate and 10% loss to follow-up, a total of 215 respondents in control/standard arm, and 152 per each of the intervention arms resulting in a total of 519. Since 519 respondents are sufficient to address the objectives of the uptake of effective contraceptives + consistent condom use, we determined that the final sample size for this study will be 519 (215 control/standard arm; 152 per each of the two intervention arms).

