At the Mulago National Referral Hospital in Kampala Uganda there are over 43,000 pregnant women seen in the antenatal clinics (ANC) and almost 30,000 deliveries each year. Routine HIV testing with pre and post counseling is provided as part of PMTCT services and almost all women are tested. The figure below shows HIV testing by age for a 2 year period from July 2012 through June 2014 from MUJHU PMTCT program data. The average HIV prevalence was 10.9% and 15 to 19 year olds represented 14% of the total women seen and tested. Of note HIV prevalence in the younger age groups largely equates to incidence of new sexually transmitted HIV infections (with the exception of the small perinatally infected population reaching reproductive age). It is perhaps self-evident that pregnant teens are expected to (and do) have a higher age-specific HIV prevalence rate than that found in the general teenage girl population as pregnant teens are both sexually active and have had unprotected sexual intercourse.

Courtesy MU-JHU PMTCT program data Nov 2014

1 in 5 (19.7%) of teens aged 15 to 19 years self-report having had a sexually transmitted infection (STIs), genital sore, ulcer or discharge in the last 12 months. However sensitivity and specificity of these signs and symptoms among women is poor. Among men sensitivity and specificity is much higher and men aged 15 to 24 reported a prevalence of 14.3%. Among both women and men aged 15 to 49 slightly more than 1 in 4 (26 and 27% respectively) sought no treatment. A study carried out among adolescents in Kampala reported prevalence of 20.6% of at least one STI.[10] Access to diagnosis and treatment services for STIs as well as uptake and effective use of dual prevention methods to prevent STIs including HIV and effective contraception for prevention of unplanned pregnancies is an important public health issue among adolescents and youth. Adolescents who have already become pregnant are a particularly high risk group for repeat unplanned pregnancies and acquisition of STIs.[5]

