	Urine	 Collect Urine (20mls) 
  Rapid test for Gonorrhea infection  Rapid test for Chlamydia infection
	Pelvic	
 • Collect vaginal swab for rapid Trichomonas vaginalis testing • Collect swab for Bacterial vaginosis testing (PH, Whiff and Clue cells)

Enhanced Peer Support Education and Counseling (Intervention)	Depending on the group the participant is randomized to, the intervention will be done around 4 weeks after enrolment as this is logistically appropriate for the study. Participants in Arm 2 will be put in homogenous groups (similar gestation, age group and language preference) of 8 – 12 adolescents, while the Arm 3 participants will schedule their individual follow-up visits on the same day as their clinic visits. Participants in the Control Arm will receive routine antenatal, delivery and follow-up services with next study visit at 3 months postpartum
Qualitative component	Participants preselected for the serial IDIs and FGDs will have the baseline interviews and FGDs within 3 weeks of enrolment prior to receiving the intervention

The participant will be provided with an appointment card (usual cards used in the ANC/PNC clinics) however a round colored sticker (different colors for each study arm) will be placed on the card to differentiate the 3 study groups.

STI treatment will be provided for any curable STI diagnosed at screening and in follow-up for the participant and her partner/s in accordance with national treatment algorithms.[33-34] Participants found to be HIV positive (by two separate rapid tests) will not be excluded from this proposed study but will be counseled, encouraged to disclose to their partner/s and will receive PMTCT services including Option B+ with ARV treatment for life as per national guidelines. As part of PMTCT services they will be encouraged to invite their partner/s for HIV C&T and their HIV-exposed infants will be followed up with linkages to ongoing services. Participants with positive syphilis tests will be treated and have repeat testing done per local national guidelines and also at the final visit.

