3.6 Study Endpoints

3.6.1 Quantitative data outcomes

Primary outcomes

1. Incidence of one or more STIs during study follow-up, with STIs confirmed by laboratory tests of HIV-1, Neisseria Gonorrhoea, Treponema pallidum (Syphilis), Chlamydia trachomatis, Bacterial Vaginosis or Trichomonas vaginalis (Composite outcome)
 - New HIV-1 diagnosis by 2 separate HIV tests with negative HIV-1 test at enrollment AND/OR
 - New Neisseria Gonorrhoea, Treponema pallidum (Syphilis), Chlamydia trachomatis, Bacterial Vaginosis or Trichomonas vaginalis test having been negative at enrollment OR with completed treatment if positive at baseline
2. Reported (and validated) consistent condom use and uptake of effective contraceptive method (Composite outcome)
 - Absence of repeat pregnancy (diagnosed by rapid urine pregnancy testing for HCG)
 - Uptake of effective contraceptive method with insertion/prescription by clinic staff from 3 months postpartum to 9 months or study completion (which ever comes 1st)
 - Self-reported consistent use of condoms during penetrative anal or vaginal sex including a) since enrollment b) since last visit c) at last penetrative sex act
 - Absence of Y-chromosome in analysis of vaginal swabs

Secondary outcomes

3. Acceptability/desirability of assigned clinic service model

Acceptability of clinic service model (composite)

- Frequency of visits
- Relevance of information to own life
- Sense of psychosocial support

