3.7.2 Statistical analysis

Exploratory data analysis will be conducted on all variables including the binary outcomes. Descriptive statistics will be generated providing proportions (percentages) for categorical data, and mean (SD)-for normally distributed data, and median (IQR) nonnormal continuous variables. A consort diagram will also be generated to show the time of enrollment, and follow-up. Bar charts showing the distribution of categorical data will also be generated. Data will be assessed for missingness especially as a result of non-follow-up in this prospective study design. In order to address this concern, a comparison of non-follow-up and those followed up will be done, and propensity scores will be constructed to use as weights in the regression models. For categorical/dichotomous outcomes, we will use Fishers Exact Test or chi-square as appropriate, and will report the respective 95% confidence intervals around point estimates, which offer important interpretation for the trial findings.

Primary outcome-1: Composite measure of consistent condom-use and use of an effective FP method. A comparison of this binary outcome will be conducted at the last follow-up. A log-

binomial regression model will be used to obtain the prevalence rate ratios (PRR) as the measure of effect or association, because the outcomes are greater than 10%. The primary exposure variable is study arm. The two intervention arms will be compared to the control arm in the same model. Potential confounders will be adjusted for, after assessing for interaction of some variables with the study-arm in the association with the primary composite outcome. Respondents from the same facility may be correlated, and so adjustment for potential clustering of observations within the selected facilities will be done.

Primary outcome-2: Incidence of any STI. Kaplan-Meier survival analysis will be conducted to determine differences in the probability of STI infection between study arms. Differences in the KM will be determined by log-rank test. Further analysis will be conducted using Poisson regression models to obtain incidence rate ratios (IRR) comparing the two intervention arms to the control arm in the same model. Potential confounders will be adjusted for, after assessing for interaction of some variables with the study-arms in the association with the incidence of STI. Adjustment for potential clustering of observations within the selected facilities will be done.

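### The 80% power for the STI outcome rests on a 20% control rate borrowed from a prevalence study and not justified for new infections after baseline testing and treatment

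*Combined protocol and SAP*

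**What the plan says.** Section 3.7.1 names the quantity used for sizing as "prevalence of STIs, at last follow-up comparing each of the two interventions to the control". Its inputs read: "For the prevalence of STIs, we assumed 20%[10] in control/standard arm, 10% in the intervention-1, and 8% in intervention-2 at the last follow-up". The plan describes these rates as an average relative reduction of 55%, and it sets power at 80%, type I error at 5% and loss at 10%. They lead to 215 control and 152 per intervention arm, 519 in all. The contraception and condom composite needed only 171 (71 + 50 + 50), so the STI calculation alone sets the trial's size.

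The 20% cites reference 10, which section 1.1 describes as follows: "A study carried out among adolescents in Kampala reported prevalence of 20.6% of at least one STI".

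The STI primary outcome in 3.6.1 is "Incidence of one or more STIs during study follow-up". A case needs a new positive test in a woman who was negative at enrolment or, for infections other than HIV, who completed treatment after a positive baseline test. Section 3.5 adds: "STI treatment will be provided for any curable STI diagnosed at screening and in follow-up for the participant and her partner/s". HIV infection at enrolment is not an exclusion (3.4.3.2), but it cannot count as a new case.

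Section 3.7.2 plans Kaplan-Meier curves with a log-rank test for this outcome, and then: "Further analysis will be conducted using Poisson regression models to obtain incidence rate ratios (IRR").

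**The concern.** The power statement and the primary outcome describe different quantities. A cross-sectional prevalence counts whatever infection is present on the survey day. The trial counts new infections from enrolment at 28 weeks of gestation or later until 6 to 9 months postpartum, in a cohort tested at entry and treated for curable infections. The two rates can differ, and the plan does not explain why 20% should serve for the second.

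The control rate is the input that drives power here. If it is wrong, the 80% is wrong for the calculation that fixed the 519, and readers of a non-significant STI result would be judging it against a power figure that the plan has not supported for that endpoint.

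**Working it through.** **Inputs.** From 3.7.1: control rate 20%, intervention rates 10% and 8% (average 9%, a 55% reduction), power 80%, alpha 5% with sidedness not stated, loss 10%, allocation 215:152:152. The ratio is √2, since 152 × 1.414 = 215. Evaluable per comparison: 215 × 0.9 = 193.5 and 152 × 0.9 = 136.8.

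**Step 1: reproduce the 519.** Two-proportion formula with pooled null variance and no continuity correction, k = 1/√2:

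n(control) = [z(α)·√(p̄(1−p̄)(1+1/k)) + z(0.80)·√(p1(1−p1) + p2(1−p2)/k)]² / (p1−p2)², with p̄ = (p1 + k·p2)/(1 + k); each arm is then divided by 0.9.

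| Reading of 3.7.1 | Control / each intervention | Total | Power of 519 |
|---|---|---|---|
| 20% vs 10%, one-sided 5% | 214 / 152 | 518 | 80.3% |
| 20% vs 9%, two-sided 5% | 219 / 156 | 531 | 79.3% |
| 20% vs 10%, two-sided 5% | 273 / 194 | 661 | 69.8% |

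The first two readings reproduce the plan's figure to within 3%, so the arithmetic is sound for its own inputs. The third does not reproduce it.

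**Step 2: power for the analysed outcome.** No control incidence is given in the documents, so 10% to 40% is assumed. All results are two-sided 5%, each intervention against control, 193.5 vs 136.8 evaluable.

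- Two proportions: power = Φ{[|p1−p2| − 1.960·s0]/s1}, where s0 is the pooled and s1 the unpooled standard error. For 20% vs 9%: pooled rate 0.1544, s0 = 0.0404, s1 = 0.0378; (0.11 − 0.0791)/0.0378 = 0.82, so power is 79%.
- Log-rank (Schoenfeld approximation): power = Φ{√(d·a(1−a))·|ln HR| − 1.960}, with HR = ln(1−p2)/ln(1−p1), a = 193.5/330.3 = 0.586, and d the expected events. For 20% vs 9%: d = 193.5 × 0.20 + 136.8 × 0.09 = 51.0, HR = 0.423; √(51.0 × 0.2426) × 0.861 − 1.960 = 1.07, so power is 86%.

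| Assumed control incidence | 55% reduction: two-proportion / log-rank | 50% reduction: two-proportion / log-rank |
|---|---|---|
| 10% | 45 / 54% | 37 / 44% |
| 15% | 65 / 73% | 55 / 62% |
| 20% | 79 / 86% | 70 / 76% |
| 25% | 89 / 93% | 82 / 86% |
| 30% | 95 / 97% | 90 / 93% |
| 40% | 99 / 99.7% | 98 / 99% |

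**Step 3: separate the two effects.** The prevalence/incidence question moves a reader up or down the rows. The 70% in the 20% row for a halved rate has another cause: it uses the plan's own rates, and the drop from 80.3% comes only from testing two-sided instead of one-sided.

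**The case against.** The strongest reply is that exit prevalence and the incident outcome largely coincide. The notes to Table 3 place STI laboratory tests at study exit and otherwise only when clinically indicated; beyond that, only HIV, and syphilis if positive at enrolment, have another scheduled test. A woman negative or treated at baseline and positive at exit is an incident case. The differences are HIV already present at enrolment, failed or uncompleted treatment, and infections found and treated between visits. If 20%, 10% and 8% were justified as cumulative incidences, the two-proportion arithmetic would not change. Section 3.7.2 also plans chi-square or Fisher tests for dichotomous outcomes. This stands, and it rules out saying that the trial was powered for something unrelated to what it analyses.

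The reply also holds on direction. A reader might infer that clearing infections at baseline pushes the control rate below 20% and leaves the trial underpowered. The documents do not support that inference. The composite counts bacterial vaginosis, infections accumulate from the third trimester to 6 to 9 months postpartum, and section 1.1 describes adolescents who are already pregnant as at particularly high risk of acquiring STIs. Each of these could put the rate above 20%. Whether the 20.6% includes bacterial vaginosis cannot be seen from the documents.

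The reply does not supply the missing justification: nothing in the plan argues for 20% as a cumulative incidence in this cohort.

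**Conclusion.** The concern holds as an unsupported assumption and a mismatch of endpoint wording. The 519 follows from the stated inputs, so there is no arithmetic error. The 80% is computed for prevalence at last follow-up with a control rate from a prevalence study, while the outcome analysed is new infection. For the plan's 55% reduction, power runs from 45% (54% by log-rank) at 10% control incidence to 99% or more at 40%. Which row applies is unknown.

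These figures assume two-sided 5% with no multiplicity adjustment, 10% loss in every arm, and a log-rank approximation.

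Sidedness is a separate matter. At the plan's own 20% vs 10%, two-sided 5% gives about 70% by two proportions (76% by log-rank), and 80% is reached only one-sided. A reader might charge that shortfall to the prevalence/incidence mismatch, but it would arise even if 20% were exactly right.

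**What to change.** Rewrite the STI part of 3.7.1 as follows.

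1. Define the sizing quantity as cumulative incidence of at least one new STI by study exit, each intervention against control.
2. Label the 20% as an assumption borrowed from a prevalence study, and give any available reason for expecting a similar, lower or higher incidence for the full composite, bacterial vaginosis included.
3. State whether the test is one- or two-sided, and report separately what this does to power at 20% vs 10%.
4. Replace the single 80% with the 10% to 40% range tabulated above, including the 55% reduction and the log-rank column that matches the planned analysis.

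This changes wording only; enrolment and study procedures stay as they are. The price is a power statement that is less definite and possibly less favourable.

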1.2 Study hypothesis and Rationale

1.2.1 Study Hypotheses

We hypothesize that there will be a significantly lower incidence of HIV/STIs and increased uptake of dual protection and effective family planning methods in the intervention groups compared to the group receiving routine care i.e. we hypothesize intervention arms will be superior to routine care for our primary outcomes.

We further hypothesize that the group peer support intervention will be superior to the individual peer support arm in achieving a secondary outcome of improved self-esteem and self-efficacy (possibly mediated through improved social connectedness and a reduced sense of isolation and internalized stigma) however our study is not powered to detect the small differences we would hypothesize in our primary outcomes of STI incidence and uptake of dual protection methods between intervention arms.

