
*Only at 3 months and study exit (month 9 or 6 for the last participants to enroll), † Pre/posttest counseling and HIV testing done only at 3 months and study exit, ‡ STI lab tests done at study exit and when clinically indicated, ¥done at 36 weeks of gestation for all study groups, ‡ done only at study exit for participants with self-reported consistent condom use

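### The 80% power in 3.7.1 has no stated sidedness; under the conventional two-sided reading of 3.7.2, the 20% v 10% STI comparison has about 70%

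*Combined protocol and SAP*

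**What the plan says.** Section 3.7.1 bases the sample size on "comparing each of the two interventions to the control in this three-arm trial". For STIs, "we assumed 20%[10] in control/standard arm, 10% in the intervention-1, and 8% in intervention-2 at the last follow-up", which the same sentence summarises as an average reduction of 55%. The design parameters follow: "With similar power of 80%, 5% type-1 error rate and 10% loss to follow-up, a total of 215 respondents in control/standard arm", with 152 in each intervention arm and 519 in total. The composite contraceptive and condom outcome needs fewer participants, so the STI outcome sets the trial size. Sidedness is not given for either outcome.

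Section 3.7.2 plans Fisher's exact or chi-square tests for dichotomous outcomes and "will report the respective 95% confidence intervals around point estimates". For STI incidence, "Differences in the KM will be determined by log-rank test", followed by Poisson models for incidence rate ratios of each intervention against control. No one-sided test or one-sided confidence limit appears. Section 1.2.1 states a directional hypothesis, "we hypothesize intervention arms will be superior to routine care for our primary outcomes", without a significance level.

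**The concern.** A 95% confidence interval and a standard chi-square, Fisher or log-rank p-value correspond to a two-sided 5% test. If the 80% in 3.7.1 was obtained some other way, the stated power does not belong to the inference that will be reported.

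If the interval or a two-sided p-value decides the result, the risk of missing the assumed 20% v 10% effect is about 30% instead of the 20% that 3.7.1 implies. A null result in that arm could then be read as stronger evidence of no effect than the design supports.

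**Working it through.** **Inputs (3.7.1).** Control rate p0 = 0.20; intervention rates p1 = 0.10 and 0.08; enrolled 215 and 152; loss 10%. Evaluable: n0 = 215 × 0.9 = 193.5 and n1 = 152 × 0.9 = 136.8. The control:intervention ratio is 215/152 = 1.414, that is √2.

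**Reproducing 215/152.** With k = 1/√2 and z_β = 0.842 for 80% power (pooled variance, no continuity correction):

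n0 = [z_α √(p̄(1−p̄)(1+1/k)) + z_β √(p0(1−p0) + p1(1−p1)/k)]² / (p0−p1)², with n1 = k·n0, then divided by 0.9 for loss.

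| Basis | Evaluable, control/intervention | After loss |
|---|---|---|
| One-sided 5%, 20% v 10% | 191.7/135.6 | about 213/151 |
| Two-sided 5%, 20% v 9% (the average) | 196.6/139.0 | about 219/155 (÷0.9) or 216/153 (×1.1) |
| Two-sided 5%, 20% v 10% | 244.5/172.9 | about 272/192 |

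The first two rows come close to 215/152 and the third does not. The stated size also matches 20% v 8% at two-sided 2.5% with a continuity correction, but only if the stated 10% loss was never applied. The text therefore does not show which route was taken.

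**Power at the stated size.**

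p̄ = (n0·p0 + n1·p1)/(n0+n1); SE0 = √[p̄(1−p̄)(1/n0+1/n1)]; SE1 = √[p0(1−p0)/n0 + p1(1−p1)/n1]; power = Φ[(p0 − p1 − z·SE0)/SE1].

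*20% v 10%:* p̄ = (38.70 + 13.68)/330.3 = 0.1586; SE0 = 0.04080; SE1 = 0.03853.
- Two-sided: (0.10 − 1.960 × 0.04080)/0.03853 = 0.520, power 69.8%.
- One-sided: (0.10 − 1.645 × 0.04080)/0.03853 = 0.853, power 80.3%.

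*20% v 8%:* p̄ = (38.70 + 10.94)/330.3 = 0.1503; SE0 = 0.03992; SE1 = 0.03694.
- Two-sided: (0.12 − 1.960 × 0.03992)/0.03694 = 1.130, power 87.1%.
- One-sided: 1.471, power 92.9%.

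*20% v 9%:* SE0 = 0.04037; SE1 = 0.03776; two-sided z = 0.818, power 79.3%. Solving for exactly 80% two-sided gives an intervention rate of 8.92%.

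**Other methods, two-sided, 20% v 10%.**
- Exact enumeration: chi-square at 194/137 gives 70.8% (88.0% for 20% v 8%); Fisher at 193/137 gives 68.2%.
- Unpooled Wald: 73.7%.
- Log-rank, simulated, 20,000 trials per scenario at 194/137. Table 3 in 3.5.1 has "STI lab tests done at study exit and when clinically indicated", so 0%, 50%, 80% or 100% of infections were placed as ties at exit and the rest spread uniformly over follow-up. Power is 70.0–71.4% (87.3–88.1% for 20% v 8%). One-sided, the figures are 80.7–81.9% and 92.9–93.6%.
- Schoenfeld: hazard ratio ln(0.90)/ln(0.80) = 0.472, with 38.7 + 13.7 = 52.4 events, gives 76.3%.
- Poisson Wald, same ratio: variance of the log rate ratio 1/38.7 + 1/13.7 = 0.099, power 66.5%.

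The log-rank, Schoenfeld and Poisson figures treat the stated prevalences as cumulative incidences.

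**Sensitivity to loss.** Pooled two-sided power for 20% v 10% is 72.3% at the 95% average retention targeted in 3.5.6, and 74.5% with no loss at all.

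**The case against.** The strongest reply is that 215/152 contains no arithmetic slip. One-sided 5% for 20% v 10% gives about 213/151, and 1.2.1 states a directional hypothesis. Alternatively, the trial may have been sized on the average 55% reduction given in the same sentence (20% to 9%), which at two-sided 5% gives 79.3% power at the stated size. Both derivations are plausible, and the documents exclude neither.

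Neither rescues the claim as written. A directional hypothesis is not a one-sided test, and if one was intended the intervals in 3.7.2 would still carry the lower, two-sided power. The average belongs to no arm, while 3.7.1 says that each intervention is compared with control. On that route the 10% arm still has about 70%.

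Three further points stand as limits. The two-sided reading is inferred: 3.7.2 never uses the term, and its interval sentence is attached to dichotomous outcomes, while the STI paragraph gives no interval level. "About 70%" is a central figure within a method range of 66.5% to 76.3%. All the figures are unadjusted: they ignore the weighting for loss, the covariate adjustment, the facility clustering, the possible month-6 exit of late enrollees (footnote to Table 1) and any multiplicity correction. Finally, the intervals planned in 3.7.2 would give readers some protection against over-reading a null result.

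**Conclusion.** The concern holds. Section 3.7.1 claims 80% power for each STI comparison without giving sidedness, and under the conventional two-sided reading of 3.7.2 that claim fails for one of the two. Power for 20% v 10% is about 70%, and it stays below 80% under every two-sided method tried after the planned loss, and under the pooled calculation even with no loss. The 20% v 8% comparison exceeds 80% on either reading in the proportion and log-rank calculations.

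The fault is a mismatch between stated power and planned inference. It is not proof that the sample size was miscalculated. The result rests on the assumed rates in 3.7.1, 10% loss, a 5% level for each comparison and no adjustment.

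**What to change.** Keep N = 519. In 3.7.1, state whether the 5% is one- or two-sided, make 3.7.2 agree, and give power separately for each comparison, labelled as an unadjusted two-proportion calculation.

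- If two-sided, suggested wording: *With 215/152/152 enrolled, 10% loss and a two-sided 5% level, unadjusted power is about 70% for 20% v 10% and about 87% for 20% v 8%.*
- If one-sided 5% was intended, say so in both sections and give about 80% and 93%. Add that the reported 95% intervals correspond to the lower two-sided powers of about 70% and 87%.

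If the average 55% reduction was the design basis, the two-sided wording applies, and that basis should also be named.

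The cost is wording only, with no extra participants and no change to data collection, though a stated figure may become less favourable. For comparison, holding 80% two-sided for 20% v 10% at the same allocation would need about 272 + 192 + 192 = 656 participants.
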